Effects of neural mobilization augmented by traditional physical therapy on pain, functional disability and H-reflex in patients after lumbar laminectomy: a randomized controlled trial

March 19, 2019

Objective: The purpose of the study was to determine whether the addition of neural mobilization to a standard postoperative physical therapy program could improve the outcome of patients after lumbar laminectomy.

Design: Randomized controlled trial with blinded evaluators.

Setting: The study was conducted in outpatient physical therapy clinic.

There are fewer studies examining physical therapy programs for post-operative rehabilitation after lumbar surgery. The aim of the current study was to establish whether the addition of neural mobilization to a standard postoperative physical therapy program is valuable for patients who had undergone lumbar decompressive laminectomy.

Methods

Participants

Sixty patients of both sexes, aged from 35-50 years who underwent lumbar laminectomy of one or two levels shared in the study. They were recruited from the orthopedic surgery and neurosurgery departments, Cairo University hospitals. The purpose and procedures were explained to each patient before participation. A signed informed consent was taken from all patients who accept participation in the study. Approval of the Research Ethical Committee of the Faculty of Physical Therapy, Cairo University was obtained (P.T.REC/012/002241). This study followed the principles of Helsinki Declaration.

Exclusion criteria

- Patients who had arthritis in the joints of the lower limbs (which would limit walking).
- Patients who had tumors, fractures or infections of the spine.
- Patients who had diabetes mellitus.
- Patients who had polyneuropathy
- Patients who had evidence of spinal cord compression.
- Patients who had previous spinal surgery, spinal stability problems (e.g. spondilo-listhesis, spondilolysis).
- Patients who had sensory loss.

Participants were randomly assigned through computer-generated random numbers into two groups. The study group consisted of 30 patients (15 females and 15 males). Patients in this group received neural mobilization in addition to a selected physical therapy program. The control group consisted of 30 patients (12 females and 18 males) and treated with the same selected physical

therapy program only. The treatment started after four weeks postoperative.²¹ All patients received their treatment three sessions/week for six successive weeks.

Outcome measures

All measurements were conducted by examiners who were blinded to the patient's group. All patients were evaluated for; 1) Leg pain intensity: It was evaluated through visual analogue scale (VAS). VAS is a 10-cm line with a "0" at the left end for "no pain" and 10 at the right end for "worst possible pain", each patient was asked to indicate on the line where his pain is in relation to the two extremes by circling the number. 2) Functional ability: It was evaluated by Oswestery disability index (ODI). The ODI is a valid and reliable tool for assessment of functional ability.

3) Nerve root compression: It was assessed through assessment of latency of H-reflex of S₁. The participant was in prone-lying position. The active recording electrode was located on the soleus between the two heads of the gastrocnemius, while reference recording electrode was located on the Achilles tendon. The stimulation was applied at the midline in the popliteal fossa on the tibial nerve. The active stimulating electrode was closer to the spine. Stimulation was performed manually every 2 seconds (sec) with a stimulus duration of 0.5 or 1.0 msec. The intensity of stimulation was increased gradually and H-reflex & M-wave were watched. The latency is measured automatically by the device from the beginning of stimulation to the beginning of the initial deflection of the H-reflex. Assessment was conducted after surgery by four weeks before starting the study (initial evaluation) and repeated after treatment (post-treatment evaluation).

[figure not shown]

Figure 1: Flow chart of participants

Physical therapy intervention

Patients in the study group received neural mobilization in the form of straight leg raising (SLR) and dorsiflexion with two-ended slider that were designed to mobilize the neural tissues. Both groups received a selected physical therapy treatment which included TENS and dynamic back and abdominal exercises.

The neural mobilization was carried out in the steps described by Butler (1991) and Shacklock (2005). The patient was in supine lying position with symmetrical alignment of his body parts and no pillow under the head. The therapist was in stride-standing beside the patient's involved side with one hand under the patient's ankle, while the other hand placed above the patient's knee joint. The therapist began to elevate the affected lower limb in a standard straight leg raising (SLR) with full knee extension until there is back pain or pain referred to the leg. Then the

therapist lowered the patient's limb few degrees. Then the therapist grasped the patient's foot and gently made dorsiflexion oscillations. Oscillations were repeated 5 to 10 times and can be repeated for 5 sets with one to two minutes rest in between sets. The amplitude of the technique can be increased gradually according to the patient tolerance and response. This technique was repeated with increasing the tension on the sciatic nerve gradually through making variations of the lower limb position as: hip adduction and hip medial rotation. These procedures were performed 3 days/week for 6 successive weeks. The total time for applying this technique was about 10 to 15 minutes according to tolerability of the patient.

Two-ended slider was used before mobilizations and repeated after the mobilization. The two-ended slider was performed from side lying position on the non-painful side with his hips and knees flexed to about 45°. The neck is moved by the therapist into flexion and extension and the patient is asked to make bilateral active knee flexion during neck flexion and make bilateral active knee extension during neck extension. The two-ended slider was performed by the same procedure from sitting position (if this is more convenient for the patient). The two-ended slider was performed five sets of five repetitions with 20 to 30 seconds rest between sets (the total time for performing the two-ended slider was about 10 minutes).

The selected physiotherapy treatment consisted of transcutaneous electrical nerve stimulation (TENSs), pelvic tilt exercises, abdominal exercises, back exercises. For TENSs application, one electrode was located over the origin of the sacral plexus and the other was located distally over the nerve trunk. The following settings for TENS was used: pulse width 260 msec, pulse frequency 150 Hz, Amplitude (or intensity) always set for the patient's comfort level. TENSs was applied for 30 minutes.

The selected exercise program included:

1) Drawing-in exercises from crook lying position: the patient was asked to contract transversus abdominus muscle and maintain contraction for 5 seconds (sec) and 5 sec rest. This exercise was repeat 5 times.

2) Raising the head from crook lying position with hold this position for 5 sec and 5 sec rest. This exercise was repeat 5 times.

3) Bridging exercises from crook lying position: the patient was asked to raise his pelvis off the plinth with hold this position for 5 sec and 5 sec rest. This exercise was repeat 5 times.

4) Raising the head and chest from prone-lying position: the patient was asked to raise his head with hold this position for 5 sec and 5 sec rest. This exercise was repeat 5 times.

5) Abdominal draw-in with double knee to chest from crook lying position: this exercise was started in the 6th week post-surgery. The patient was asked to bring his knees to his chest with maintain abdominal draw in throughout the entire exercise with maintaining this position for 5 sec. This exercise was repeat 5 times with 5 sec rest in between.

6) Alternately raising one limb from quadruped position: this started at the 7th week post-surgery. From quadruped position with maintaining the head and back straight, the patient was instructed to raise one upper limb till horizontal level and hold this position for 5 seconds then return it. Then he was asked to repeat this with the other upper limb after 5 seconds of rest then return. After that, the patient was asked to repeat this with one lower limb, then with the other lower limb after 5 seconds of rest. This exercise was repeat 2 times.

7) Alternately raising two opposite limbs from quadruped position at the same time: this exercise was started at the 9th week post-surgery. From quadruped position with maintaining the head and back straight, the patient was instructed to raise both one upper limb with the opposite lower limb simultaneously till horizontal level and hold this position for 5 seconds then return them. Then, the patient was asked to repeat this with the other two limbs. This exercise was repeat 2 times.

Each the previous sets of exercises was done 5 sets with 30 seconds rest in between sets. During exercises, patients were instructed to keep normal respiration and avoid holding of breathing. The selected exercises was done for a total of 30 to 45 minutes according to the types of exercises given to the patient.

Effects of neural mobilization augmented by traditional physical therapy on pain, functional disability and H-reflex in patients after lumbar laminectomy: a randomized controlled trial

Statistical Analysis

March 19, 2019

Sample size

The sample size was calculated prior to the study. Calculation was performed using G*POWER statistical software [F tests- MANOVA: Repeated measures, within-between interaction, $\alpha=0.05$, $\beta=0.2$, effect size = 0.37] and revealed that the required sample was N=60.

Statistical analysis

All statistical analysis was out using the Statistical Package for Social Studies (SPSS) version 25 for windows (IBM SPSS, Chicago, IL, USA).

Descriptive statistics and t-test were conducted for comparison of subject characteristics between both groups.

Chi- squared test was used for comparison of sex distribution. Shapiro–Wilk test was used to explore the normality of data. Levene’s test was used to check the homogeneity between groups.

Mixed MANOVA was conducted to compare within and between groups effects on visual analogue scale (VAS), Oswestry Disability Index (ODI) and H-reflex latency. Post-hoc tests using the Bonferroni correction were performed for subsequent multiple comparison. The level of significance for all statistical tests was set at $p < 0.05$.

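### Does describing leg pain as a 10-cm VAS, yet having patients circle a number, undermine the planned analysis?

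*Combined protocol and SAP*

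**What the plan says.** In the protocol, under Outcome measures, the first outcome is leg pain intensity. The instrument is introduced with "VAS is a 10-cm line with a" zero at the left end and ten at the right. The response instruction follows in the same sentence: "each patient was asked to indicate on the line where his pain is in relation to the two extremes by circling the number". The two end anchors are the only numerals described, and no scoring rule or recording unit is given. The same section says that examiners were blinded to group and that assessment took place before and after treatment, with one response mode for everyone.

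In the SAP, under Statistical analysis, the normality check is a single statement: "Shapiro–Wilk test was used to explore the normality of data". It names no variable, does not say whether groups or visits are pooled, and gives no consequence of a rejection. Leg pain then enters the main analysis under the VAS label, together with ODI and H-reflex latency: "Mixed MANOVA was conducted to compare within and between groups effects on visual analogue scale (VAS"). All tests use the 0.05 level.

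**The concern.** A VAS is scored as the distance from the left end to the patient's mark, which gives a nearly continuous value. Circling a printed number gives one of eleven whole numbers. The protocol's sentence mixes the two, and no other section settles which was used.

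Two things could be at stake. First, if numerals were circled, one of the three MANOVA outcomes would be reported under the wrong instrument name. Second, the Shapiro-Wilk test is sensitive to ties. Whole-number scores could fail it even when the underlying pain is normal, and the SAP does not say how a failure should be read. One might also fear that coarse scoring costs power in a trial of only 60 patients.

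**Working it through.** **Inputs from the documents.** The SAP's Sample size section gives "within-between interaction, $\alpha=0.05$, $\beta=0.2$, effect size = 0.37" and "revealed that the required sample was N=60". The Participants section gives 30 per group ("The study group consisted of 30 patients", and the same number of controls). There are two visits.

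**Assumed inputs.** The documents give no mean, SD or pre-post correlation r for leg pain. The ranges used are means of 2 to 6, SDs of 0.75 to 2.5 and r of 0.3 to 0.7. Simulated scores are normal, clipped to 0-10, and rounded either to 0.1 cm (measured line) or to whole numbers (circled numeral). The checks treat leg pain on its own, not the three-outcome multivariate test.

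**1. The plan's sample size.** For a within-between interaction with two groups and two measurements, λ = f²N = 0.37² × 60 = 8.214, with 1 and 58 degrees of freedom. Power is 0.805 at N = 60 and 0.798 at N = 59, so 60 is reproduced exactly. The effect size has no unit, so the scoring form does not enter the calculation.

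**2. Type I error.** A two-sample t-test with 30 per arm was run on 20,000 simulated trials per setting.
- Single scores, mean 3, SD 0.75 to 2.0: 0.048-0.051 with whole numbers and 0.049-0.051 with 0.1-cm readings.
- Whole-number change scores, SD 1.5 and 2.5, r 0.3 and 0.7: 0.048-0.052.

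**3. Precision.** Rounding to whole numbers adds a variance of about 1/12 per reading, so 2/12 to a change score whose variance is 2·SD²(1 − r). The relative inflation is (1/12) / [SD²(1 − r)].
- Smallest: SD 2.5, r 0.3: 0.0833 / (6.25 × 0.7) = 1.9%.
- Largest: SD 1.5, r 0.7: 0.0833 / (2.25 × 0.3) = 12.3%.

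A comparison with power 0.80 on unrounded change scores would have 0.793 in the first case and 0.753 in the second. For single scores at d = 2 × 0.37 = 0.74, simulated power with whole numbers is 0.75, 0.77, 0.79 and 0.80 at SD 0.75, 1.0, 1.5 and 2.0. With 0.1-cm readings it is 0.80-0.81.

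**4. Shapiro-Wilk at 0.05, n = 30.** The table shows the share of samples rejected (5,000 samples per row; in the SD 2.5 row, 5,000 trials with means within 0.5 of 5).

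| Mean | SD | Whole number | 0.1 cm |
|---|---|---|---|
| 5 | 1.0 | 96% | 5% |
| 5 | 1.5 | 45% | 5% |
| 5 | 2.0 | 18% | 4% |
| 5 | 2.5 | 12% | 3-4% |
| 3 | 1.5 | 45% | 4% |
| 3 | 2.0 | 38% | 11% |
| 2 | 1.5 | 85% | 21% |
| 2 | 2.0 | 89% | 59% |

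If the test were run separately in each of the four group-by-visit cells, at least one rejection would occur as follows.
- Means near 5, SD 1.5: 89-91% of trials with whole numbers, against 18% with 0.1-cm readings.
- Means near 5, SD 2.0: 55-57% against 13%.
- Baseline mean 6, post-treatment mean 2, SD 2.0, r 0.5: 99% against 84%.

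The SAP does not say that the check is made by cell, so these four-cell rates rest on an assumed procedure.

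**5. What the plan does with the check.** It uses the test to explore. No transformation, rank-based substitute or change of model depends on the result. A rejection and a non-rejection lead to the same mixed MANOVA.

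**The case for a change.** The strongest case for acting is that leg pain is one of only three outcomes, that the response instruction cannot be followed literally unless intermediate numerals were printed, and that a reader cannot reconstruct the score. Ties alone could produce a significant Shapiro-Wilk result, which an analyst might take as a reason to abandon the planned model. A sentence of clarification would cost almost nothing.

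Part of this stands. The wording is ambiguous, an 11-point rating is the likelier reading, and at SDs up to about 1.5 the scoring form has a large effect on the rejection rate. The rest does not carry through:

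- The instrument-name point is conditional. Loose wording for marking a line is also possible, and the documents cannot show which form was used.
- The contrast with a 3-5% rejection rate for measured readings holds when scores stay clear of the floor. Lower pain after treatment is plausible, and at mean 2 and SD 2.0 measured readings fail in 59% of samples as well.
- Abandoning the MANOVA after a rejection would depart from the written plan. The absence of a stated response to a failed check concerns all three outcomes and does not arise from circled numbers.

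**Conclusion.** No change to the plan is needed. This is a gap in description that analysts fill without difficulty: each patient contributes one score between 0 and 10 per visit, obtained in the same way in both groups by blinded examiners, and that score goes into the mixed MANOVA whichever form was used. N = 60 is unaffected, type I error stays at 0.048-0.052, and the largest power loss in the grid is about 5 to 6 percentage points (0.80 to 0.75), at its extremes: SD 1.5 with r 0.7 for change scores, or SD 0.75 for single scores. The raised Shapiro-Wilk rejection rate is real under mid-scale assumptions, but it leads to no decision in the SAP. These figures rest on assumed means, SDs and correlations and on a single-outcome check. Stating the response form and unit when results are reported would help readers, but it would not alter the analysis or its conclusion.

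### Does the plan need to say which leg's S1 H-reflex latency enters the mixed MANOVA?

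*Combined protocol and SAP*

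**What the plan says.** The third outcome in the Outcome measures section is introduced as "Nerve root compression: It was assessed through assessment of latency of H-reflex" of S1. The text gives the patient's position, the recording site ("The active recording electrode was located on the soleus between the two heads of the gastrocnemius"), the stimulation site ("The stimulation was applied at the midline in the popliteal fossa on the tibial nerve"), the stimulus rate and duration, and how the latency is read. It names neither left or right nor affected or unaffected. Assessment is done before treatment and repeated afterwards, by examiners who do not know the group.

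Side appears only under Physical therapy intervention. For the straight-leg raise, given to the study group only, "The therapist began to elevate the affected lower limb". The two-ended slider is done in "side lying position on the non-painful side". The TENS text for both groups names no side: "one electrode was located over the origin of the sacral plexus and the other was located distally over the nerve trunk".

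The Statistical analysis section says: "Mixed MANOVA was conducted to compare within and between groups effects on visual analogue scale (VAS), Oswestry Disability Index (ODI) and H-reflex latency". It does not say whether the latency is from one leg, the mean of both, or a difference between legs.

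**The concern.** Every patient has two legs, and the model takes one latency per visit. The affected leg, a fixed side and the mean of both legs are three different variables, and the same patients could give different answers on each. The exclusion criteria do not remove patients with pain in both legs, and for them the word affected does not pick out a leg.

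Two things could be at stake. If some patients were measured on a leg that responds less to treatment, the effect on latency would be diluted. If both legs were recorded and the choice was left open, a leg could be chosen after the results were seen, which raises the false-positive rate for latency and for the joint test. A reader also cannot confirm from the text that the leg measured is the leg mobilised.

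**Working it through.** **The plan's own figure.** Inputs from the Sample size section: alpha 0.05, power 0.80, effect size f = 0.37, and a repeated-measures MANOVA for the within-between interaction. There are two groups and, taken from the Outcome measures section, two visits. The noncentrality is N·f² = 60 × 0.37² = 8.21 on 1 and 58 degrees of freedom. Power is 0.805, and 60 is the smallest N that reaches 0.80. The stated N reproduces. The plan ties f = 0.37 to no particular outcome; below it is placed on the affected leg.

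**Dilution (hypothetical).** Let q be the share of patients measured on the other leg, and k the effect in that leg divided by the effect in the affected leg. Neither is in the documents. With the SD unchanged, f = 0.37 × [(1 − q) + q·k].

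| q | k = 0 | k = 0.5 | k = 1 |
|---|---|---|---|
| 0 | 0.805 | 0.805 | 0.805 |
| 0.25 | 0.561 | 0.694 | 0.805 |
| 0.50 | 0.291 | 0.561 | 0.805 |

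For example, q = 0.50 and k = 0 give f = 0.37 × 0.5 = 0.185, noncentrality 60 × 0.185² = 2.05 and power 0.291.

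**Mean of both legs (hypothetical).** Let rho be the between-leg correlation of change, also assumed. Then f = 0.37 × [(1 + k)/2] / √[(1 + rho)/2]. Power at k = 0 / 0.5 / 1 is 0.370 / 0.685 / 0.902 for rho = 0.5, and 0.304 / 0.583 / 0.824 for rho = 0.9. The mean does worse than the affected leg when k is small and better when k = 1.

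**Free choice of leg (hypothetical).** Simulation of change scores, 30 per arm, no true effect, 40,000 runs. Taking the smaller p-value of the two legs gives a type I error of about 0.09 (rho = 0.5) or 0.07 (rho = 0.9). In a joint test of the three outcomes (assumed correlations: pain with disability 0.5, each with latency 0.3), choosing between legs gives about 0.07 or 0.06, against about 0.05 with a fixed leg.

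**Which rows do the documents support?**

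- *Which leg.* The outcome is labelled as root compression, and leg pain intensity is scored in all patients. A symptomatic leg can therefore be identified in controls as well, without the mobilization text. One recording set-up and one latency are described. All of this points to the affected leg, q = 0.
- *Same leg twice.* The assessment is described as repeated, which in ordinary use means the same measurement again.
- *Is k = 0 plausible?* The slider, done before and after the mobilization for about 10 minutes, has the patient bend and straighten both knees. The study treatment is not confined to one limb, so no effect at all in the other leg is an extreme assumption.
- *Were both legs recorded, and one chosen later?* Nothing in the documents suggests it.

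**The case for a change.** The strongest opposing case is that the affected leg is an inference. The recording method is specified down to the stimulus duration, yet the side is missing; H-reflex is in the trial title and is one of three variables in the main test; and two or three lines would close the gap. Patients with pain in both legs have no rule even under the natural reading. The type I error figures, unlike the power figures, do not depend on k.

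The omission stands, including the gap for symptoms in both legs. The harm does not follow from it. Allocation is random and the examiners are blinded, so any single fixed rule gives a valid comparison of the arms, and so does any choice for a patient with both legs painful that is made from initial findings. The type I figures require two premises with no support in the text: that both legs were recorded, and that the choice followed the results. The single-outcome figures also bypass the planned joint test. If latency were claimed only when the joint test was significant too, choosing between legs with no effect on any outcome would give about 0.03. The SAP states no such gate, and that protection weakens if pain or disability truly differ.

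The eligibility wording, "who underwent lumbar laminectomy of one or two levels shared in the study", concerns surgical levels and does not bear on which leg is tested.

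**Conclusion.** No change to the plan is needed. The documents do not name the leg, do not state that it is the same at both visits, and give no rule for symptoms in both legs. This is missing detail that a competent analyst fills in one sensible way: the affected leg, the same one before and after treatment, chosen alike in both arms. On that reading the comparison is valid, power stays at 0.805 with N = 60, and the loss is zero.

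The losses shown above depend on assumed values of q, k and rho, or on a choice of leg after the results were seen. None of these comes from the documents, so the figures measure how large a departure would have to be and are not estimates of harm in this trial. The conclusion rests on the affected leg having been used, or another rule fixed without regard to group or results. The ordinary place to name the leg is the description of methods in the trial report; the design, the sample size and the analysis would be the same either way.

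### Do the TENS pulse width and frequency, which cannot both hold as printed, call for a change to the plan?

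*Combined protocol and SAP*

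**What the plan says.** The Physical therapy intervention section of the combined protocol and SAP describes the background programme and gives the TENS settings as "pulse width 260 msec, pulse frequency 150 Hz". The same paragraph gives the electrode sites, leaves intensity to the patient's comfort, and fixes the session length: "TENSs was applied for 30 minutes". The opening of that section makes clear that TENS is not part of the experimental contrast: "Both groups received a selected physical therapy treatment which included TENS and dynamic back and abdominal exercises". Neural mobilization is what the study group receives in addition.

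The abbreviation msec appears in one other place, in the H-reflex description under Outcome measures: "Stimulation was performed manually every 2 seconds (sec) with a stimulus duration of 0.5 or 1.0 msec". Nothing else in the document restates the TENS pulse width or frequency, and no burst or modulated mode is described.

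**The concern.** The two settings stand in one sentence and are presented as used together, yet a pulse cannot last longer than the cycle it belongs to. Read literally, the pair is physically impossible, so at least one figure or unit must be wrong. Width and frequency are also the only electrical parameters the plan fixes, since amplitude is left to comfort.

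What seemed to be at stake was the description of the comparator. The trial asks what neural mobilization adds to a standard programme, and a reader who wants to repeat or interpret that programme cannot set a device from this line. If therapists had filled the gap differently, the background treatment might also have varied. The document contains no sign that they did, so that remains conjecture.

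**Working it through.** **Inputs.** Pulse width w = 260 ms = 0.260 s and pulse frequency f = 150 Hz, both from the TENS sentence under Physical therapy intervention. Milliseconds is the literal reading of msec.

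**Can the printed frequency be reproduced from the printed width?** For pulses that do not overlap, w must not exceed the period 1/f.

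- Period at the stated frequency: 1000/150 = 6.67 ms. This is the longest possible pulse.
- Highest frequency at the stated width: 1/0.260 = 3.85 Hz.
- Pulse time needed in each second: 150 × 0.260 = 39 s.
- Mismatch: 260/6.67 = 39, and equally 150/3.85 = 39.

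The stated 150 Hz is therefore not reproduced.

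**Could rounding explain it?** A width between 259.5 and 260.5 ms gives a ceiling of 3.85 to 3.84 Hz. A frequency between 149.5 and 150.5 Hz gives a period of 6.69 to 6.64 ms. Neither comes near closing the gap.

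**Does the other use of the unit help?** The H-reflex stimulus is given "with a stimulus duration of 0.5 or 1.0 msec", once every 2 seconds. A 1.0 ms stimulus in a 2000 ms interval is possible, so milliseconds works there. That is evidence of how the abbreviation is used in that place. It does not show what the source page prints in the TENS sentence.

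**Does either figure reach the inference?** The Sample size section uses alpha 0.05, beta 0.2 and "effect size = 0.37] and revealed that the required sample was N=60". For two groups and two assessments (initial and post-treatment), the noncentrality is 0.37² × 60 = 0.1369 × 60 = 8.21 on 1 and 58 degrees of freedom. Power is then 0.805, and 60 is the smallest N that reaches 0.80. The stated sample size reproduces without any TENS parameter. The Statistical analysis section takes VAS, ODI and H-reflex latency into a mixed MANOVA by group and time, and TENS settings are not a term in it.

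**The case for a change.** The strongest case for acting is that the contradiction is real on the page, that nothing elsewhere in the document resolves it, and that correcting it would cost one line. A misread symbol should not simply be assumed either: the same conversion kept the Greek letters in the sample-size line, the subscript in the H-reflex description and the degree sign in the slider description. A reader's guess at the intended setting is no substitute for a stated one.

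Most of that stands. The arithmetic is certain on the milliseconds reading, and the cause cannot be settled from the extracted text: a slip in the source and a misread symbol are both possible.

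The step from there to a defect in the plan does not stand. It would be too much to say that the TENS component cannot be delivered or replicated, because electrode placement, comfort-level amplitude and the 30-minute duration are untouched; only the width and frequency pair fails. The factor of 39 measures overlap under one reading of the unit and says nothing about consequence for any outcome. The document also reports the treatment in the past tense. A machine accepts only a possible pair, so the settings in use were necessarily something other than what is printed. Correcting the line would improve the record without altering what was done or how it is analysed.

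**Conclusion.** This is a clerical slip, in the source or in the conversion of the PDF, and it calls for no change to the plan. As printed, 260 ms and 150 Hz conflict by a factor of 39. The two figures and their units must be reconciled against the source page and, if the conflict is there too, against the device settings used. This review takes no view on which is right.

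The correction gains nothing for the trial's design or inference. TENS belongs to the programme shared by both groups, so the misprint does not by itself separate the arms. The sample size of 60, the three outcomes, the mixed MANOVA and the conclusion drawn from it would read the same after the line was put right.

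Three conditions underlie this. First, msec is read as milliseconds; if the source page shows a consistent pair, even the clerical point disappears. Second, the same settings were used in both groups, as the document says. Third, nothing in the document suggests that settings varied between therapists or that any patient was wrongly treated, and the misprint is not evidence of either.

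### The mixed MANOVA has no baseline covariate, so the per-outcome treatment test is a valid change-score comparison that is usually less precise than a baseline-adjusted one

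*Combined protocol and SAP*

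**What the plan says.** Under Outcome measures, leg pain (VAS), function (ODI) and S1 H-reflex latency each have two assessments: "Assessment was conducted after surgery by four weeks before starting the study (initial evaluation) and repeated after treatment (post-treatment evaluation".

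Under Sample size, the test is "F tests- MANOVA: Repeated measures, within-between interaction", with "effect size = 0.37] and revealed that the required sample was N=60".

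Under Statistical analysis, the only outcome model is this: "Mixed MANOVA was conducted to compare within and between groups effects on visual analogue scale (VAS), Oswestry Disability Index (ODI) and H-reflex latency". It is followed by "Post-hoc tests using the Bonferroni correction were performed for subsequent multiple comparison". That sentence does not say which contrasts are meant or over which family the correction runs.

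No covariate, ANCOVA or other baseline adjustment appears anywhere. The t-tests and chi-squared test on patient characteristics describe the groups and do not feed the outcome model. The initial value of each outcome enters only as one level of the time factor.

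**The concern.** With two groups and two time points, the group-by-time interaction for one outcome is a two-sample comparison of change. Taking change fixes the slope of post on baseline at 1. A linear model with baseline as covariate estimates that slope, and so removes more noise unless the true slope is close to 1.

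The plan also does not say which term carries the treatment comparison. Its wording on between-group effects could be read as the group main effect, which averages pre and post values and so dilutes the treatment effect. It could also be read as an unnamed post-only contrast among the post-hoc tests. Neither is adjusted for baseline.

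What is at stake is the width of the confidence intervals, and some power, for each of three outcomes in a trial of 60 patients. Validity is not at stake.

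**Working it through.** **Inputs from the documents.** Alpha 0.05, beta 0.2, effect size 0.37 and N=60 (Sample size); two groups of 30 (Participants); two assessments (Outcome measures).

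**Assumptions.** The documents give no SDs or rho. I take equal pre and post SDs, rho from 0.3 to 0.9, and a true effect held at the value that gives the planned effect size on change.

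**1. Reproduce the plan's N.** For two groups and two times, the interaction is an F test on 1 and N−2 df with noncentrality f²N = 0.37² × 60 = 8.21. Power is 80.5% at N=60 and 79.1% at N=58, so the stated N is reproduced. It is the same test as a two-sample t-test on change with d = 2 × 0.37 = 0.74.

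**2. Compare with baseline adjustment.** In units of the post SD:
- Change-score variance factor: 2(1−rho). The true effect is 0.74 × √(2(1−rho)) = 0.876/0.740/0.573/0.331 at rho 0.3/0.5/0.7/0.9.
- ANCOVA variance factor: (1−rho²) × (1 + 1/(N−4)). The last term is the expected cost of estimating the slope, 57/56 at N=60. The test has 57 df.
- Ratio of ANCOVA to change-score variance: (1+rho)/2 × 57/56.

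| rho | variance ratio | 95% CI width ratio | ANCOVA power, alpha 0.05 | ANCOVA power, alpha 0.0167 |
|---|---|---|---|---|
| 0.3 | 0.662 | 0.81 | 93.4% | 85.1% |
| 0.5 | 0.763 | 0.87 | 89.7% | 78.9% |
| 0.7 | 0.865 | 0.93 | 85.7% | 72.9% |
| 0.9 | 0.967 | 0.98 | 81.7% | 67.3% |
| Change score, any rho | 1 | 1 | 80.5% | 65.6% |

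The last column applies if the Bonferroni correction runs across the three outcomes (0.05/3). Simulation with fitted models, 200,000 trials per rho at alpha 0.05, agrees: ANCOVA 93.3/89.7/85.7/81.7%, change score 80.5–80.6%, and type I error 4.9–5.1% for both.

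**3. Patient equivalents.** The smallest N at which ANCOVA matches the change score at 60 satisfies (1+rho)/2 × (N−3)/(N−4) × 60/N ≤ 1. This gives 40.09/46.07/52.07/58.06, which rounds up to 41/47/53/59.

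**4. Where the gain ends.**
- Equal SDs: the ratio reaches 1 at rho = 2 × 56/57 − 1 = 0.965.
- Unequal SDs, with k the post SD over the pre SD: the ratio is k²(1−rho²)(57/56) / (1 + k² − 2·rho·k).
- At k=1.5 and rho 0.7 this is 2.25 × 0.51 × 1.0179 / 1.15 = 1.016, with power 79.8% against 80.5%.
- At k=0.75 the ratio is 0.47–0.57 over rho 0.3–0.9, so the gain is larger than with equal SDs.
- The worst ratio is 57/56 = 1.018, a loss under 2% of variance.

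**5. The group main effect.** The average of pre and post carries half the treatment effect, with variance factor (1+rho)/2. At rho 0.5 the standardised effect is 0.37/√0.75 = 0.427, and power is about 37%.

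**6. Running both tests without a rule.** If either the change-score test or ANCOVA could be claimed at 0.05, simulation under no effect (40,000 trials per rho, one outcome) gives false-positive rates of 7.8/7.5/6.8/6.1% at rho 0.3/0.5/0.7/0.9.

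**The case against.** The strongest reply is that nothing is wrong. The trial is sized on the interaction, the mixed MANOVA contains that term, the N is reproduced, and the test holds its 5% level. That stands in full, and it is why the point is of modest severity.

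A second reply is that the size of the gain rests on values the documents do not give. That also stands. The direction is secure over most of the range, but the gain is about one percentage point of power at rho 0.9, and there is none near rho 0.7 if the post SD is 1.5 times the pre SD. It does not defeat the point, because the slope is estimated from the data and the worst loss is under 2% of variance.

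Third, the text is largely in the past tense and gives realised counts, such as "The study group consisted of 30 patients (15 females and 15 males", so the trial may be complete. That limits what can be changed, and the fix allows for it.

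A reader might infer more than this, and the documents do not support it:
- **That the planned analysis is biased or invalid.** Patients are randomised, and in simulation the unadjusted estimates are unbiased with correct type I error.
- **That the trial is underpowered for its planned test.** At the stated inputs it has 80.5% power. The 65.6% applies only if the correction is 0.05/3, a family the plan does not specify.
- **That power falls to 24.3%.** That is the post-only contrast at rho 0.9. The plan never names this contrast as its treatment test, and the sample-size statement points to the interaction.
- **That ANCOVA beats the joint three-outcome MANOVA test.** No such comparison was made.

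**Conclusion.** The point holds as an efficiency improvement of modest severity. With equal pre and post SDs and the planned effect, adjusting for baseline narrows the per-outcome 95% CI by about 19/13/7/2% at rho 0.3/0.5/0.7/0.9 relative to the change score. At alpha 0.05 it raises power from 80.5% by about 13/9/5/1 percentage points. The advantage also appears at 0.0167. Confidence is high in the direction of the gain over most of the range, but its size for these three outcomes is unknown because it depends on SDs and correlations that the documents do not report. The lack of a named treatment term is a related ambiguity, and the same edit resolves it.

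**What to change.** **If outcome data have not been seen.** For each of VAS, ODI and H-reflex latency, make the deciding per-outcome comparison a linear model of the post-treatment value on randomised group, with that outcome's baseline value as covariate. It replaces the unadjusted per-outcome comparison. Test it at the plan's Bonferroni level across the three outcomes, and report the adjusted difference with its 95% CI. Report the mixed MANOVA as supportive only, with the group-by-time interaction named as its treatment test, so that a positive result cannot be claimed from whichever analysis succeeds.

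**If outcome data have been seen.** The planned interaction stays the deciding test. Report the baseline-adjusted analysis beside it as a sensitivity analysis, labelled post hoc.

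**Cost.** One SAP paragraph and one degree of freedom per model, with no new data or patients; the model can be fitted in SPSS 25, which the plan already names. The downside is a possible precision loss of under 2% of variance where the slope of post on baseline is close to 1.
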